## 9.4 Pharmacodynamic Analyses

### 9.4.1 Pharmacodynamic Parameter Estimation

Patients who receive at least 1 dose of study drug and have evaluable PD data will be included in the analysis set for the PD analyses.

Data will be analysed for the patients during each MMTT. The change from baseline values (the average of -30, -15 and 0 minutes represented as the 0-hour time point following the start of the MMTT) for each patient will be calculated. The  $\Delta AUC[0-1h]$ , area under the baseline subtracted glucose concentration versus time curve from time 0 to 2 hours post-meal ( $\Delta AUC[0-2h]$ ) and area under the baseline subtracted glucose concentration versus time curve from time 0 to 5 hours post-meal ( $\Delta AUC[0-5h]$ ) will be calculated. In addition, the change from baseline maximum glucose observed during the 5 hours post-meal and change from baseline 1 hour glucose and 2 hour glucose after the start of the meal will be calculated. Other partial  $\Delta AUCs$  may be calculated, as deemed appropriate.

For those patients which received treatment (insulin or glucose) for hypoglycemic or hyperglycemic events, the postprandial glucose collected post intervention during the MMTT following will not be included in the glucodynamic assessment. These glucose parameters will be analyzed in 2 different ways:

- 1) the glucose values collected prior to any treatment intervention due to hypoglycemic or hyperglycemic event. Glucose values collected after intervention were treated as missing in the datafile;
- 2) last observation carried forward (LOCF): the last observed glucose values prior to treatment intervention due to hypoglycemic or hyperglycemic event were carried forward to the end of the MMTT timing.

In addition, a graphical comparison of the “normal” glucose response following the MMTT from healthy subjects to the glucose response following administration of these insulin analogues (LY900014, Humalog, FIASP or NovoRapid) in patients with T1DM will be presented.

Parameters will be individually calculated for each patient and presented by summary statistics.

#### **9.4.2 Pharmacodynamic Statistical Inference**

Patients who did not complete the entire meal or had significant changes in nutrient consumption of the standardised test meal or dose changes during the MMTTs will be excluded from all the statistical analysis of the PD parameters.

Summary statistics (including number of patients, mean, standard deviation or standard error, minimum and maximum) will be presented by treatment. All PD parameters (including  $\Delta$ AUCs, glucose changes from baseline and time parameters) on the original scale (not log transformed) will be analysed using a statistical model that includes treatment, sequence and period as fixed effects and patient within sequence as a random effect. The p-value on the difference between LSmeans will be used to determine statistical significance and the corresponding 95% CIs for the LSmean ratios from Fieller’s theorem will be presented.

Statistical significance will be achieved when the p-value for a test is less than 0.05. The primary comparison will be of LY900014 to Humalog. The following comparisons will also be performed.

- LY900014 versus FIASP
- LY900014 versus NovoRapid
- Humalog versus NovoRapid

No multiplicity adjustment will be done for the above pair comparisons.

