5.1.1.3. Inpatient Procedures

Run-In

On the day before each MMTT day (that is, Day -1 in each of the 4 periods), patients will arrive at the CRU in the early evening (approximately 1700 hours) except for patients who undergo the dose-finding assessment from Day -2 of Period 1. Patients will be advised to bring their prandial insulin when they arrive at the CRU, which will be administered before the start of a standardised dinner.

Before the start of the run-in period, cannulation of 2 veins will be performed. A variable IV infusion of glucose (20% dextrose solution) and/or insulin glulisine will be initiated (~2400 hours) in order to obtain a blood glucose target level of 135 ± 15 mg/dL (7.5 ± 0.8 mmol/L). Any insulin infusion should be tapered off and stopped at least 30 minutes prior to start of the standardised test meal. For the last 30 minutes prior to study drug administration, the target blood glucose concentration should be within the range without any glucose infusion. If this target blood glucose range is not attained before 1100 hours, the meal test will be halted and may be performed on a separate visit; each meal test can only be repeated once (see Section 6.2.3 for rescheduling).

Study MMTT

Each patient's individual, short-acting insulin may be administered on Day -1 before the start of a standardised dinner (at approximately 1900 hours). If a correction dose of short-acting insulin needs to be administered after the meal, no more than 6 U of short-acting insulin should be administered between 7 and 12 hours before the scheduled intake of standardised test meal.

The meal test may start in the early morning at approximately 0700 hours with allowance up to 1100 hours, if required, to ensure the patient's blood glucose level is stable and on target, with the pre-meal activities as specified in the Schedule of Activities (Section 2). LY900014, Humalog, FIASP, or NovoRapid SC bolus injection will be administered immediately before the start of MMTT during each of the 4 treatment periods according to the randomisation schedule. The individualised dose for each patient will be the same for all the 4 treatment periods. For each MMTT, the patient should stay in a semi-supine position for 2 hours post-meal. The patient will not be allowed to consume water for 2 hours after the MMTT assessment begins; however, water may be consumed freely 2 hours post-meal.

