10.3. Statistical Analyses

Statistical analysis of this study will be the responsibility of Eli Lilly and Company or its designee.

Primary statistical analyses of PK and PD parameters for the cohort of patients with T1DM will be conducted on the set of patients who complete all treatment periods with identical prandial insulin doses for the MMTTs during the study, as the PK parameters and PD response is dependent on the insulin dose which is individualised for each patient. Supportive analyses may be done on the key parameters for the patients who complete at least 2 treatment periods.

Any change to the data analysis methods described in the protocol will require an amendment only if it changes a principal feature of the protocol. Any other change to the data analysis methods described in the protocol and the justification for making the change will be described in the study results.

Safety analyses will be conducted on the set of patients receiving at least 1 dose of the study drug to which they are randomised, regardless of whether or not they completed all protocol requirements.

Unless otherwise noted, all tests of treatment effects will be conducted at a 2-sided alpha level of 0.05, and CIs will be calculated at 95%, 2-sided. No multiplicity test adjustment will be made for secondary objectives.

Additional exploratory analyses of the data will be conducted as deemed appropriate.

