10.3.3.2. Pharmacodynamic Statistical Inference

Patients who did not complete the entire meal or had significant changes in nutrient consumption of the standardised test meal or dose changes during the MMTTs will be excluded from all the statistical analysis of the PD parameters.

Summary statistics (including number of patients, mean, standard deviation or standard error, minimum and maximum) will be presented by treatment. All PD parameters (including ΔAUC s, glucose changes from baseline and time parameters) on the original scale (not log transformed) will be analysed using a statistical model that includes treatment, sequence and period as fixed

effects and patient within sequence as a random effect. The p-value on the difference between LSmeans will be used to determine statistical significance and the corresponding 95% CIs for the LSmean ratios from Fieller's theorem will be presented.

Statistical significance will be achieved when the p-value for a test is less than 0.05. The primary comparison will be of LY900014 to Humalog. The following comparison will also be performed.

- LY900014 versus FIASP
- LY900014 versus NovoRapid
- Humalog versus NovoRapid

No multiplicity adjustment will be done for the above pair comparisons.

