## 7. SAMPLE SIZE JUSTIFICATION

An initial 74 patients with T1DM may be enrolled so that approximately 64 patients complete the study. Sixty-four completing patients will provide at least 95% power to demonstrate a 2-fold increase in the serum insulin lispro AUC from time 0 to 30 minutes (AUC[0-30min]) between LY900014 and the Humalog. Testing will be done at an alpha level of 0.05 with a 2-sided confidence interval (CI). The sample size will also provide greater than 95% power to demonstrate a 35% reduction of early 50%  $t_{max}$  between LY900014 and Humalog. The estimated standard deviation of within-subject difference on the log scale is 0.35 for AUC(0-30min) and 0.3 for early 50%  $t_{max}$ , according to an analysis of internal Lilly data (Study I8B-FW-ITRG) for LY900014 and Humalog administered in a repeat-dose study.

With this sample size, there is more than 95% power to detect a 40% reduction in postprandial glucose incremental area under the baseline subtracted glucose concentration versus time curve from time 0 to 1 hour ( $\Delta$ AUC[0-1h]) between LY900014 and Humalog. With similar assumptions, the study is also adequately powered for the comparison between LY900014 and NovoRapid.

With 64 completing patients, there is more than 95% power to detect a 20% reduction of early 50%  $t_{max}$  between LY900014 and FIASP. In addition, there is approximately 80% power to demonstrate a 25% reduction in postprandial glucose incremental AUC from time 0 to 1 hour between LY900014 and FIASP. The power calculation is based on published results of FIASP studies and internal Lilly data.

Patients who are randomised but drop out before completing assigned treatment may be replaced to ensure that approximately 64 patients complete the study.

For the healthy cohort, 12 non-diabetic healthy subjects will be evaluated for their glucose and insulin secretory response to the MMTT. No treatment will be provided for this cohort. The sample size for the healthy cohort was chosen to provide sufficient data in order to evaluate the objectives of the study, and is not intended to achieve any a priori statistical requirements.

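### The PD model subtracts each period's baseline glucose but has no baseline term, so the slope is fixed at 1; adding the covariate is a nearly free, probably small, gain in precision

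*SAP*

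**What the plan says.** SAP 9.4.1 forms a separate baseline in each MMTT, "the average of -30, -15 and 0 minutes represented as the 0-hour time point following the start of the MMTT", and subtracts it to obtain ΔAUC(0-1h), ΔAUC(0-2h), ΔAUC(0-5h) and the changes from baseline. Protocol 10.3.3.1 does the same.

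The SAP 9.4.2 model for all these parameters "includes treatment, sequence and period as fixed effects and patient within sequence as a random effect". The matching sentence in protocol 10.3.3.2 also "includes treatment, sequence and period as fixed" effects, with patient within sequence random. Neither document plans a baseline covariate or a baseline-adjusted sensitivity analysis.

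Baseline is controlled by design. Protocol 5.1.1.3 sets an overnight IV run-in to 135 ± 15 mg/dL and adds: "For the last 30 minutes prior to study drug administration, the target blood glucose concentration should be within the range without any glucose infusion". It continues: "If this target blood glucose range is not attained before 1100 hours, the meal test will be halted".

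On power, SAP section 7 (and protocol 10.1) gives, for ΔAUC(0-1h) with 64 completers, more than 95% for a 40% reduction against Humalog and about 80% for a 25% reduction against FIASP. No SD is given for any ΔAUC.

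**The concern.** Subtracting baseline and then fitting no baseline term assumes that a patient who starts one MMTT 10 mg/dL higher than another stays 10 mg/dL higher throughout the window. If the true within-patient slope is β, the amount (1 − β) × baseline deviation × window length remains in ΔAUC. The patient random effect cannot absorb it, because baseline differs between periods within a patient. Error in the three-sample mean acts the same way, since it lowers the slope on the observed baseline.

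There is some reason to expect a slope below 1. The three samples fall in the last 30 minutes before the meal, just after a variable insulin or glucose infusion, so part of a deviation may be transient. The meal then supplies about 100 g of carbohydrate. A slope of exactly 1 is least plausible over five hours.

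At stake is the precision of the secondary PD endpoints, ΔAUC(0-1h) and ΔAUC(0-5h). It matters most for LY900014 versus FIASP, the glucose contrast planned with the least power.

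**Working it through.** **Inputs from the documents.** Two-sided alpha 0.05 (protocol 10.3); 64 completers (SAP section 7); ΔAUC(0-1h) power of about 80% at a 25% reduction and more than 95% at 40% (SAP section 7); baseline target 135 ± 15 mg/dL (protocol 5.1.1.3).

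**Assumed, not in the documents.** Mean ΔAUC(0-1h) 40-80 mg·h/dL; within-patient baseline SD 3-8.7 mg/dL; true slope β from 0 to 1. The upper SD is a uniform spread over the whole target window: 30/√12 = 8.7.

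**Step 1: the plan's own figures.** Without a ΔAUC SD the stated power cannot be reproduced independently, so I solved for the SD of the paired difference that gives 80% at 25%.
- Normal approximation: 0.25 × √64 / (1.960 + 0.842) = 0.714 of the comparator mean.
- Noncentral t, 63 df: 0.703 of the mean.
- With 0.703, power at a 40% reduction is 99.4%. The two stated ΔAUC figures are therefore consistent with each other.

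**Step 2: share of within-patient variance that the covariate can remove, 0-1 h window.**

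Share = [(1 − β) × baseline SD × 1 h]² / (0.703 × mean / √2)²

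The within-patient SD is 0.703 × 40/√2 = 19.9 at mean 40 and 39.8 at mean 80. Example: β = 0.5, SD 8.7, mean 40 gives (4.35/19.9)² = 4.8%.

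**Step 3: power for the 25% reduction, with the SD multiplied by √(1 − share).** The range runs over the assumed means and baseline SDs.

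| True slope β | Share removed | LY900014 vs FIASP power |
|---|---|---|
| 1 | 0% | 80.0% |
| 0.8 | 0.02-0.8% | 80.0-80.3% |
| 0.5 | 0.1-4.8% | 80.1-81.9% |
| 0 | 0.6-19.1% | 80.2-87.6% |

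Power for the 40% Humalog contrast is 99.4% at β = 1 and 99.4-99.9% across the other rows.

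These limits depend on the assumed mean. At a mean of 30 mg·h/dL with baseline SD 8.7, the normal approximation gives about 83% at β = 0.5 and 93% at β = 0.

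**Step 4: five-hour window.** The residual term per period is (1 − β) × baseline SD × 5 h:
- β = 0.8: 3 to 9 mg·h/dL
- β = 0.5: 7.5 to 22 mg·h/dL
- β = 0: 15 to 44 mg·h/dL

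No ΔAUC(0-5h) SD is stated, so no variance share or power follows.

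**Step 5: what the covariate costs if it is not needed.** Simulation with 64 patients, a 4×4 Williams design, assumed mean ΔAUC(0-1h) 45 mg·h/dL, within-patient SD 22.7 and baseline SD 8.7. SE of the treatment difference, without and with the covariate:
- β = 1: 3.99 and 4.02
- β = 0.8: 3.96 and 3.97
- β = 0.5: 3.90 and 3.79
- β = 0: 4.00 and 3.72

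The true difference was −11.25. Mean estimates in these runs lay between −11.17 and −11.39, with no sign of bias in either model.

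**The case against.** The strongest reply is that baseline is already handled twice: the run-in holds it near a common value, and subtraction removes it at slope 1. If the slope is near 1, as it may well be in the first hour, the covariate gains nothing. This stands, and it is why the likely gain for ΔAUC(0-1h) is small. It does not remove the point: two valid periods in one patient can still differ by up to 30 mg/dL, and slope 1 is assumed rather than checked.

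The 8.7 mg/dL upper SD counts the whole permitted window as within-patient variation, although some of that spread would lie between patients. That also stands, so the upper ends of the ranges are generous.

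The FIASP contrast is not the main one. SAP 9.4.2 makes LY900014 versus Humalog the primary comparison, and on the back-solved SD its ΔAUC(0-1h) power is already about 99%. This is correct.

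Finally, a period-varying covariate in a random-patient model mixes within- and between-patient slopes. That is a fair technical objection, and splitting the covariate answers it.

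A reader might go further and infer that the plan ignores baseline, that lost precision is established, or that chance baseline differences bias the treatment estimates. The documents support none of these. Baseline is subtracted. No baseline SD, ΔAUC SD or slope is given from which a loss could be shown. Sequence allocation is randomised and baseline is pre-dose, so only (1 − β) of a chance difference carries over, and the model's SE already reflects it.

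**Conclusion.** The point holds as a free improvement, not a defect of validity. Subtraction without a baseline term fixes the within-patient slope at 1, and any departure from that adds to the residual.

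For ΔAUC(0-1h) against FIASP the gain is about 0 to 2 percentage points of power if the slope is 0.5 or more. The 88% figure needs three extremes together: no relation between post-meal glucose and baseline, a baseline SD of 8.7 and the lowest assumed mean. It should not be read as the expected gain. For Humalog the gain is negligible. ΔAUC(0-5h) is where a gain is most plausible, but its size cannot be derived from the documents.

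All of this rests on the SD back-solved from the stated 80% power and on the assumed means, baseline SDs and slopes.

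**What to change.** In SAP 9.4.2, pre-specify a baseline-adjusted model for the ΔAUC and change-from-baseline parameters:
- Add two covariates: the deviation of the period's baseline (mean of −30, −15 and 0 min) from the patient's own mean baseline, and that patient mean.
- Report LSmeans at the common mean baseline, and use them for the differences and the Fieller ratios.
- Keep the unadjusted model as a named sensitivity analysis.
- Record the change in SAP section 11, which now states that nothing differs from the protocol.

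The cost is a few lines of SAP text and two model terms, with no new data. In the simulation the SE rose from 3.99 to 4.02 when the covariate was not needed. It is best settled at SAP sign-off, which SAP section 3 places before first dosing. Adjustment chosen later would be a supplementary analysis, and protocol 7.3 leaves the sponsor unblinded, so the choice of model could be questioned.

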### **9.5 Safety and Tolerability Assessments**

#### **9.5.1 Adverse events**

Where changes in severity are recorded in the Case Report Form (CRF), each separate severity of the adverse event (AE) will be reported in the listings, only the most severe will be used in the summary tables. A pre-existing condition is defined as an AE that starts before the subject has provided written informed consent and is ongoing at consent. A non-treatment emergent AE is defined as an AE which starts after informed consent but prior to dosing. A treatment-emergent AE is defined as an AE which occurs postdose or which is present prior to dosing and becomes more severe postdose.

All AEs will be listed. Treatment-emergent AEs will be summarized by treatment, severity and relationship to the study drug. The frequency (the number of AEs, the number of subjects experiencing an AE and the percentage of subjects experiencing an AE) of treatment-emergent AEs will be summarized by treatment, Medical Dictionary for Regulatory Activities (MedDRA) version 20.1 system organ class and preferred term. The summary and frequency AE tables will be presented for all causalities and those considered related to the study drug. Any serious AEs will be tabulated.

### **9.5.2 Concomitant medication**

Concomitant medication will be coded using the WHO drug dictionary (Version September 2017). Concomitant medication will be listed.

### **9.5.3 Clinical laboratory parameters**

All clinical chemistry, hematology and urinalysis data will be listed. Additionally clinical chemistry, hematology and urinalysis data outside the reference ranges will be listed.

Values for any clinical chemistry, hematology and urinalysis values outside the reference ranges will be flagged on the individual subject data listings.

### **9.5.4 Vital signs**

Vital signs data will be listed for individual subjects.

### **9.5.5 Hepatic Monitoring**

If a subject experiences elevated alanine aminotransferase (ALT)  $\geq 3 \times$  upper limit of normal (ULN), alkaline phosphatase (ALP)  $\geq 2 \times$  ULN, or elevated total bilirubin (TBL)  $\geq 2 \times$  ULN, liver tests will be performed to confirm the abnormality.

The subjects' liver disease history and associated person liver disease history data will be listed. Any concomitant medication of acetaminophen/paracetamol will be listed. Results from any hepatic monitoring procedures, such as a magnetic resonance elastography (MRE) scan, and a biopsy assessment will be listed, if performed.

Hepatic risk factor assessment data will be listed. Liver related signs and symptoms data will be summarized by treatment and listed. Alcohol and recreational drug use data will also be listed.

All hepatic chemistry, hematology, coagulation, and serology data will be listed. Values outside the reference ranges will be flagged on the individual subject data listings.

### **9.5.6 Blood Glucose Monitoring and Hypoglycemia**

Hypoglycemic events will be appropriately recorded in the CRF. In the case of a hypoglycemic event, the actual blood glucose value, if measured, will be recorded in the CRF, together with any treatments administered. Each category of hypoglycemic events (defined below) will be listed and summarized by treatment during study and during MMTT.

Hypoglycemia is defined as follows:

- **Documented Glucose Alert Level (Level 1)**, Plasma Glucose (PG)  $\leq 70$  mg/dL (3.9 mmol/L):
  - **Symptomatic hypoglycemia**: an event during which typical symptoms of hypoglycemia are accompanied by PG  $\leq 70$  mg/dL (3.9 mmol/L)
  - **Asymptomatic hypoglycemia**: an event not accompanied by typical symptoms of hypoglycemia but with PG  $\leq 70$  mg/dL (3.9 mmol/L)
  - **Unspecified hypoglycemia**: an event during which PG  $\leq 70$  mg/dL (3.9 mmol/L) but no information relative to symptoms of hypoglycemia was recorded
- **Documented Clinically Significant Hypoglycemia (Level 2)** PG  $< 54$  mg/dL (3.0 mmol/L):
  - **Symptomatic hypoglycemia**: an event during which typical symptoms of hypoglycemia are accompanied by PG  $< 54$  mg/dL (3.0 mmol/L)
  - **Asymptomatic hypoglycemia**: an event not accompanied by typical symptoms of hypoglycemia but with PG  $< 54$  mg/dL (3.0 mmol/L)
  - **Unspecified hypoglycemia**: an event during which PG  $< 54$  mg/dL (3.0 mmol/L) but no information relative to symptoms of hypoglycemia was recorded
- **Severe hypoglycemia (Level 3)**: an event requiring assistance of another person to actively administer carbohydrate, glucagon, or other resuscitative actions. During these episodes, the patient has an altered mental status and cannot assist in their care, is semiconscious or unconscious, or experienced coma with or without seizures and may require parenteral therapy. PG measurements may not be available during such an event, but neurological recovery attributable to the restoration of blood glucose concentration to normal is considered sufficient evidence that the event was induced by a low PG concentration (PG  $\leq 70$  mg/dL [3.9 mmol/L])
  - **Severe hypoglycemia requiring medical attention**: a severe hypoglycemic event when patients require therapy by HCPs (EMTs, emergency room personnel, etc)

